7.3. Removal of Subjects from Study Therapy

A subject may be removed from the study therapy for a variety of reasons, including:

- Unacceptable adverse event
- Subject unwilling or refusal to continue with the protocol defined study visits and/or consent withdrawal for study participation
- Change in compliance with an inclusion/exclusion criteria
- General or specific changes in the subject's condition that render the subject unacceptable for further treatment in this study in the judgement of the investigator.

If a subject is to be withdrawn from the study, the Aclaris Therapeutics, Inc. CRA or designee must be informed within 24 hours of the decision to remove the subject from the study.

Aclaris Therapeutics, Inc.

Protocol Number: A-101-WART-303

Protocol: Version 3: 14 February 2019

The study may be discontinued at the discretion of Aclaris Therapeutics, Inc. Some examples of reasons for discontinuation are the occurrence of the following:

- Increased frequency, severity or duration of known AEs
- Medical, regulatory or ethical reasons affecting the continued performance of the study
- Difficulties in the recruitment of subjects

7.4. Withdrawal Procedures

If a subject withdraws from the study prior to Day 182 (6-month time-point), the reason for withdrawal and the date of withdrawal from the study must be recorded on the eCRF. If the reason for withdrawal is an adverse event or a clinically significant abnormal laboratory test result, monitoring of the subject will continue until the event has resolved or stabilized, until the patient is referred to the care of a local health care professional, or until a determination of a cause unrelated to the study drug or study procedure is made.

7.5. Subject Replacement

Subjects that are determined to be screen failures may be rescreened for the study and if determined to be eligible for the study they may be randomized using the same subject identifier. A screen failure is a subject that signs an informed consent form for participation in the study but is determined not to be eligible for the study prior to the subject being randomized to the study.

7.6. Subject Identifier (SI)

The investigator or designee will assign a unique eight-digit subject identifier (SI) to each subject at Visit 1.

The SI format will be NNN-NN-NNN where the first 3 digits associate the subject with either the 301 or 302 study, the middle 2 digits are the investigational center site number (using leading zeroes, as appropriate) and the final 3 digits are the subject number which was assigned during the parent study. For example, the SI for the second subject previously treated on the A-101-WART-301 study that signs an informed consent at site number 04 would be 301- 04-002.

The subject will be identified using the SI in all study documentation for the duration of the study.

Aclaris Therapeutics, Inc.

Protocol Number: A-101-WART-303

Protocol: Version 3: 14 February 2019

8. STUDY PROCEDURES

The schedule of study activities (including assessments, tests, exams, disease assessments, and study drug administration) beginning with screening and continuing through the end of study are outlined in [Table 2](#) and [Table 3](#). A written, signed informed consent form (ICF) must be obtained from each subject prior to performing any study related procedure.

Aclaris Therapeutics, Inc.

Protocol Number: A-101-WART-303

Protocol: Version 3: 14 February 2019

Table 2: Study Procedures for Subjects with Common Warts at Visit 1

Visit	V1	V2	V3	V4	V5	V6	V7	EOS
Visit Day	Day 1	Day 15	Day 29	Day 43	Day 60	Day 102	Day 144	Day 182
Visit Windows		+3 Days	+ 3 Days	+ 3 Days	+ 3 Days	+ 3 Days	+ 3 Days	+ 2 Days
In Office Visit	▲ ¹		▲		▲			▲
Phone Call		▲ ⁴		▲ ⁴		▲ ⁴	▲ ⁴	
Informed Consent	▲							
Inclusion Criteria/Exclusion Criteria	▲							
Clinical Chem / CBC ²								▲
Common Wart Identification	▲ ³							
Common Wart Dimensions	▲		▲		▲			▲
Physician's Wart Assessment	▲		▲		▲			▲
Local Skin Reactions	▲		▲		▲			▲
Study Medication Application ⁵	▲	▲	▲	▲				
Study Medication Dispensing and Instructions for at home application	▲		▲		▲ ⁶			

Aclaris Therapeutics, Inc.

Protocol Number: A-101-WART-303

Protocol: Version 3: 14 February 2019

Visit	V1	V2	V3	V4	V5	V6	V7	EOS
Concomitant therapies		▲	▲	▲	▲	▲	▲	▲
Adverse Events	▲	▲	▲	▲	▲	▲	▲	▲

¹Visit 1 of A-101-WART 303 may occur on the same day as Visit 13 of A-101-WART 301 or A-101-WART 302.

² Subjects who do not have their Visit 1 assessment on Visit 13 of A-101-WART 301 or A-101-WART-302 will have to have a clinical chemistry and a complete blood count drawn and sent to the central laboratory for analysis. A complete blood count (including hematocrit, hemoglobin, platelet count, red blood cell count and morphology, white blood cell count and differential (absolute and %) including basophils, eosinophils, lymphocytes, monocytes and neutrophils and a clinical chemistry panel including albumin, alkaline phosphatase, alanine aminotransferase (ALT), aspartate aminotransferase (AST), blood urea nitrogen (BUN), bicarbonate, calcium, chloride, creatinine, glucose, lactate dehydrogenase (LDH), phosphorus, potassium, sodium, total bilirubin, total protein, and uric acid.

³ Warts that are identified for treatment must meet the requirements as outlined in Section 9.1.

⁴ Investigational site staff will be required to make a phone contact with the subject on Day 15, Day 43, Day 102 and Day 144 to assess for any safety issues and possible new concomitant medications the subject may have started taking. In addition, subjects are to ask if they have had any new warts develop since the last in office visit.

⁵ Subjects over the age of 18 are to apply the A-101 study medication on the following days: Day 1, Day 4, Day 8, Day 11, Day 15, Day 18, Day 22, Day 25, Day 29, Day 32, Day 36, Day 39, Day 43, Day 46, Day 50 and Day 53. A window of +1 day is allowed. Subject between the ages of 1-17 will have their A-101 study medication applied by a parent or guardian. Parents/legal guardians of children must ensure that the child does not put the treated area in their mouth, or eyes, until completely dry after the application. If the treated area is not completely dry 10 minutes after the application, the area should be blotted dry.

⁶ A-101 will only be dispensed to subjects who have not cleared all their warts, or who have developed new warts, and will be starting a new 8-week treatment cycle.

Table 3 Safety Observation Assessments for Subjects that are Clear at Visit 1 and Remain Clear

Visit	V1	V2	V3	V4	EOS
Treatment Day	Day 1	Week 6 (Day 42)	Week 12 (Day 84)	Week 18 (Day 126)	Week 26 (Day 182)
Window		+7 Days	+ 7 Days	+ 7 Days	+ 2 Days
In Office Visit	▲ ¹				▲

Aclaris Therapeutics, Inc.

Protocol Number: A-101-WART-303

Protocol: Version 3: 14 February 2019

Visit	V1	V2	V3	V4	EOS
Phone Call		▲ ²	▲ ²	▲ ²	
Informed Consent	▲				
Inclusion Criteria/Exclusion Criteria	▲				
Concomitant therapies		▲	▲	▲	▲
Adverse Events	▲	▲	▲	▲	▲

¹Visit 1 of A-101-WART 303 may occur on the same day as Visit 13 of A-101-WART 301 or A-101-WART 302.

² Investigational site staff will contact via a documented phone call on Visit 2 Day 42, Visit 3 Day 84, Visit 4 Day 126 and Visit 5 Day 182. During the phone calls sites are to ask the subject if they have had any new warts develop or if a wart that was previously treated has recurred. If a subject has had a new wart develop or a previously treated wart has recurred, then the subject is to be scheduled for an in -office visit to start an 8-week treatment course with A-101 study medication. Subjects are to be instructed to contact the investigational site as soon as they think a new wart (or a recurrence) has developed. The 8-week treatment period can start no later than Day 122. Refer to Table 2 for the 8- week treatment schedule.

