5.1.2. Secondary Objectives

The secondary objectives of this study include:

- Efficacy of A-101 45% in the treatment of recurrent and/or further treatments for new warts
- Duration of response of A-101 45%
- Onset of action of A-101 45%

Aclaris Therapeutics, Inc.

Protocol Number: A-101-WART-303

Protocol: Version 3: 14 February 2019

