9.2. Common Wart Dimensions and Physician's Wart Assessment (PWA)

Each identified wart that will be treated with A-101 study medication will be measured using the Aclaris supplied ruler. The longest axis of each identified wart will be documented on the subject's eCRF.

The Physician's Wart Assessment (PWA) is the Investigator's assessment of the severity of each identified common wart at a particular time-point. The Investigator should NOT refer to any other assessments to assist with this evaluation. This evaluation IS NOT a comparison with the PWA performed at any other visit.

During an 8-week treatment period, subjects will have their identified warts assessed using the PWA at the following time-points: Day 1, Day 29, Day 60 and Day 182.

The Investigator will assess each identified common wart and report the one integer that best describes the common wart severity using the following scale.

Physician's Wart Assessment	
Grade	Descriptor
0	Clear: No visible wart. No further treatment is indicated
1	Near Clear: a visible wart that is less than 3 mm in maximal diameter (or length)
2	A visible wart \geq 3 mm and $<$ 6 mm in maximal diameter (or length)
3	A visible wart \geq 6 mm in maximal diameter (or length)

The physician is encouraged to use a ruler or caliper and to feel the wart or skin area to help his/her assessment.

Common warts that are assessed by the investigator as having cleared (PWA =0) will be instructed not to continue to apply the A-101 study medication.

Refer to [Appendix 2](#) for the PWA Site Manual.

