14.3. Statistical Analysis of Efficacy

Unless otherwise stated, all efficacy summaries and analyses will be conducted using the ITT population. All efficacy summaries and analyses will be produced for the following groups:

- Subjects treated in the study that were randomized to active treatment during the previous A101-WART 301/302 study.
- Subjects treated in the study that were randomized to vehicle during the previous A101-WART 301/302 study.
- Subjects treated in the study overall.
- Subjects not requiring treatment during the study that were randomized to active treatment during the previous A101-WART 301/302 study.
- Subjects not requiring treatment during the study that were randomized to vehicle during the previous A101-WART 301/302 study.
- Subjects not requiring treatment in the study overall.
- All subjects combined

The primary efficacy analysis will be the effectiveness of A-101 45% based on the proportion of subjects who achieve complete clearance (PWA=0) of all identified common warts at any scheduled visit. Any identified common wart for a subject that has missing PWA data will be treated as not clear for the purpose of the primary efficacy analysis.

Four secondary efficacy analyses will be performed:

- Durability of response: for warts achieving a status of Clear (PWA=0), the number of weeks the wart remains clear will be tabulated and these results will be summarized using descriptive statistics. The proportion of these warts that remain clear at the end of the study will also be presented.
- Mean per-subject percent of treated warts that are Clear (PWA=0) at each visit will be summarized using descriptive statistics.
- Proportion of subjects with a single wart at baseline whose wart is Clear (PWA=0) will be summarized using descriptive statistics by visit.
- Median time to achieve onset of Clearance (PWA=0) for all treated warts.

Efficacy summaries will be supported by listings of PWA data.

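### Subjects who enter clear and stay untreated have no scheduled investigator wart assessment, and the SAP leaves them out of the duration-of-response summaries

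*Protocol*

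**What the plan says.** Protocol Section 8 has two schedules. Table 2 covers subjects with warts and includes PWA rows. Section 9.2 confirms that during a treatment period "subjects will have their identified warts assessed using the PWA at the following time-points: Day 1, Day 29, Day 60 and Day 182". Table 3, "Safety Observation Assessments for Subjects that are Clear at Visit 1 and Remain Clear", has rows for the office visit, phone calls, consent, eligibility, concomitant therapies and adverse events, and nothing else. The SAP reproduces it with the same rows.

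Protocol 5.1.2 lists "Duration of response of A-101 45" (the 45% solution) among the secondary objectives. Protocol 14.3 asks for every efficacy analysis in seven groups. Three of these are untreated in this study: "Subjects not requiring treatment during the study that were randomized to active treatment during the previous A101-WART 301/302 study", the matching vehicle group, and "Subjects not requiring treatment in the study overall". The primary efficacy measure is "the proportion of subjects who achieve complete clearance (PWA=0) of all identified common warts at any scheduled visit", and the four secondary analyses also start from PWA=0.

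The SAP takes a different course. Section 3.1 runs efficacy on subjects with at least one application of study medication. Section 3.2 displays only the two open-label treated groups for that population. Section 3.14 declares the change and says that data from untreated subjects will be listed.

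**The concern.** The subjects on Table 3 are those whose warts had gone by the end of the parent study and who are then observed for about six months without treatment. They bear directly on how long a response lasts. Their status is never scored in this study: the site asks by phone whether a wart has appeared, and the subject answers.

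The move to the Safety population adds a selection problem. A subject who entered clear joins that population only by developing a wart and starting treatment. One who stays clear to Day 182 never joins. Membership of the efficacy population is thus decided by the outcome of interest, and the subjects with lasting clearance are the ones left out. The proportion remaining clear at end of study in SAP 3.10.2.1 will not include them.

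**Working it through.** **1. The schedules side by side**

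| | Table 2 (warts present) | Table 3 (clear, untreated) |
|---|---|---|
| PWA at Visit 1 | Yes | No |
| PWA after Visit 1 | Days 29, 60, 182 (3) | None (0) |
| Day 182 visit | In office | In office by the table mark; footnote 2 lists it as a phone call |
| How recurrence is found | PWA, plus calls | Calls on Days 42, 84 and 126, or contact started by the subject |

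The Day 182 conflict lies within Table 3. Section 9.3 lists calls only on Days 42, 84 and 126, and Section 12.2 requires Day 182 blood samples from all subjects. Both fit an office visit, although Table 3 has no laboratory row.

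**2. Whether another route supplies an investigator score**

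- A wart reported early leads to an office visit and, if a course starts, to all Table 2 assessments (Section 9.3).
- No course may start after Day 122, so the Day 126 call falls 4 days too late. From then to end of study is 182 − 122 = 60 days, in which a reported wart triggers no scheduled PWA. The SAP copy of the footnote gives Day 102 as the last start, which would make it 182 − 102 = 80 days. The two documents must be reconciled.
- The synopsis names skin examinations among the safety evaluations, but Table 3 contains none.

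**3. Who enters the SAP's durability summaries**

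- Entered with warts, treated: in the Safety population, PWA at Days 29, 60 and 182. Included.
- Entered clear, developed a wart, treated: in the Safety population from then on. Included.
- Entered clear, stayed clear: no application in this study, so not in the Safety population. Listed only.

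**4. How many subjects**

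Inputs from Protocol 14.1 and SAP 3.13: 400 enrolled, 200 of them previously on active treatment, 26% of warts clear at the end of the parent studies.

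- The plan's own figure: 200 × (1 − 0.26) = 148 needing treatment. It reproduces exactly.
- The complement: 200 × 0.26 = 52 previously active subjects clear at entry.
- The 26% is a proportion of warts, which the plan applies to subjects. A subject is clear only if every wart is. As an assumed example, with two warts per subject the count runs from 200 × 0.26² ≈ 14 (independent warts) to 52 (fully correlated).
- Vehicle clearance is not given. Assuming 0% to 26%, and keeping the plan's simplification, the total clear at entry is 52 to 52 + 200 × 0.26 = 104, or 13% to 26% of 400.

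**5. What an end-of-study PWA would give (illustration only)**

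If 42 of 52 were still clear (assumed), the proportion would be 81%, with an exact 95% interval of 0.675 to 0.904. If 5 of those 42 had warts that they did not report, the true figure would be 37/52 = 71%, and the present schedule could not show the difference. The interval describes sampling precision; it does not measure error from self-report, for which the documents give no figure.

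**The case against.** The strongest reply is that the SAP governs and has already dealt with this. Protocol Section 14 leaves analysis details to the SAP, and SAP 3.14 states and explains the change. A reader might infer from Protocol 14.3 and Table 3 alone that the report will contain PWA tables with no data. The SAP does not support that: untreated groups are not displayed for efficacy.

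A reader might also infer that the whole duration-of-response objective rests on self-report. That does not hold either. Durability after clearance in this study is analysed in treated subjects, whose Table 2 schedule ends with an investigator score at Day 182. For a single course, the interval from Day 60 to Day 182 has phone contact only, but the closing status is scored.

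Third, the primary objective is safety, Table 3 is titled as safety observation, and Section 9.2 applies the PWA to identified warts, which these subjects do not have. Recurrence is sought at three calls, and subjects are told to contact the site as soon as they suspect a wart. Under-reporting is possible but not quantified. This makes the schedule an understandable choice.

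These replies narrow the point to subjects who enter clear and stay untreated. They do not answer it for them: the SAP change avoids an empty table by removing these subjects, and a stated secondary objective loses its untreated responders.

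**Conclusion.** The point holds for subjects clear at Visit 1 who remain untreated. They have no scheduled investigator assessment of clearance, and the SAP excludes those who stay clear from every duration-of-response summary. Protocol 14.3 and the SAP also still differ on the untreated groups, although the SAP says so openly.

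The size is roughly 52 previously active subjects clear at entry, resting on the plan's use of a wart-level 26% for subjects. It may be well below that if many subjects had several warts, and it rises to at most 104 in all if vehicle clearance is assumed to be up to 26%. It would be wrong to read 52 as the number without any scored endpoint, because those who recur and start a course move to Table 2 and are then scored.

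Safety conclusions and durability in treated subjects are unaffected. The change is worth making because it serves a stated objective cheaply; the study does not fail without it.

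**What to change.** 1. **Protocol Table 3, its copy in the SAP, and Section 9.2:** add a PWA at end of study, and at Visit 1 unless it was done that day at parent Visit 13. Score each previously treated site as 0 or above 0 and note any new warts. Subject numbers carry over from the parent study (Section 7.6), so sites can be linked to the parent record.
2. **SAP 3.1, 3.2 and 3.10.2.1:** define a set of all subjects clear at Visit 1. Report by parent arm the proportion still clear at Day 182. Keep those who recurred and moved to Table 2 in the denominator, counted as not remaining clear; otherwise the proportion describes only those left on Table 3. Missing assessments can follow the SAP 3.10.1 convention (not clear, with observed data as sensitivity). Update SAP 3.14, and bring Protocol 14.3 into line with the result.
3. **Reconcile** Table 3 footnote 2 (Day 182 as a call) with the in-office mark and Section 12.2, and the Day 122 and Day 102 limits between the two documents.

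The cost is a small amendment to protocol, CRF and SAP, and a few minutes of investigator time at Day 182, provided that visit is confirmed as in-office. If the sponsor prefers not to add the assessment, the minimum is to remove the untreated efficacy groups from Protocol 14.3 and state that durability in these subjects is not assessed. That settles the mismatch but leaves the objective without them.

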9. STUDY ASSESSMENTS

9.1. Identification of Common Warts

Subjects who have completed participation in the A-101-WART 301 or A-101-WART-302 study are eligible to enroll into the A-101-WART -303 study. Subjects that were previously treated on the double-blind phase 3 study whose warts have recurred, were not treated or who develop new warts during the observation period of A-101-WART -303 are also eligible to receive treatment with A-101 Topical Solution 45% twice a week for 8 weeks. An 8-week treatment period may begin anytime between Day 1 and Day 122.

Warts that are identified by the treating investigator must meet the following criteria:

- Subject may have 1 wart and up to 6 common warts treated during an 8-week treatment period
- Identified warts must have a longest axis of ≤ 8 mm.
- Be a discrete lesion, i.e. each wart meeting the entry criteria must be clearly separated from other warts
- Not be a periungual, subungual, genital, anal, mosaic, plantar, flat or filiform wart
- Not be in an intertriginous fold
- Not be covered with hair which, in the Investigator's opinion, would interfere with the study medication treatments or the study evaluations

Not be in an area that may be occluded (e.g., by clothing or footwear or in a skin fold).

Each identified wart will be identified on the body charts in the subject's eCRF.

9.2. Common Wart Dimensions and Physician's Wart Assessment (PWA)

Each identified wart that will be treated with A-101 study medication will be measured using the Aclaris supplied ruler. The longest axis of each identified wart will be documented on the subject's eCRF.

The Physician's Wart Assessment (PWA) is the Investigator's assessment of the severity of each identified common wart at a particular time-point. The Investigator should NOT refer to any other assessments to assist with this evaluation. This evaluation IS NOT a comparison with the PWA performed at any other visit.

During an 8-week treatment period, subjects will have their identified warts assessed using the PWA at the following time-points: Day 1, Day 29, Day 60 and Day 182.

The Investigator will assess each identified common wart and report the one integer that best describes the common wart severity using the following scale.

Physician's Wart Assessment	
Grade	Descriptor
0	Clear: No visible wart. No further treatment is indicated
1	Near Clear: a visible wart that is less than 3 mm in maximal diameter (or length)
2	A visible wart \geq 3 mm and $<$ 6 mm in maximal diameter (or length)
3	A visible wart \geq 6 mm in maximal diameter (or length)

The physician is encouraged to use a ruler or caliper and to feel the wart or skin area to help his/her assessment.

Common warts that are assessed by the investigator as having cleared (PWA =0) will be instructed not to continue to apply the A-101 study medication.

Refer to [Appendix 2](#) for the PWA Site Manual.

9.3. Phone Call Visits

Subjects that are enrolled to the study that do not have any identified warts to be treated will complete the Visit 1 (can be the same day as V13 of A-101-WART-301 or A-101-WART-302) assessment in the office and then will have telephone contact visits on Day 42, Day 84, and Day 126. During these calls site staff will ask the subject if they have any adverse events that they feel are related to their previous treatment with A-101 Topical Solution and if they have had a new wart develop or if they have had a recurrence of a wart that was previously treated on the A-101-WART 301 or A-101-WART 302 study. If a subject has a new wart or a recurrence they can be scheduled for an in-office visit and initiate treatment on another 8-week treatment period with A-101 study medication. If an 8-week treatment period is started then all assessments outlined in Table 2 must be followed. A subject cannot start an 8-week treatment period after study Day 122.

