13. ADVERSE EVENTS

13.1. Definitions

13.1.1. Adverse Events (AEs)

An adverse event (AE) is any untoward medical occurrence in a patient that develops or worsens in severity during the conduct of a clinical study of a pharmaceutical product and does not necessarily have a causal relationship to the study drug. An adverse event can, therefore, be any unfavorable and unintended physical sign, symptom, or laboratory parameter that develops or worsens in severity during the course of the study, or significant worsening of the disease under study (or any concurrent disease), whether or not considered related to the study drug.

Accordingly, an adverse event could include any of the following:

- intercurrent illnesses;
- physical injuries;
- events possibly related to concomitant medication;
- significant worsening (change in nature, severity, or frequency) of the disease under study or other pre-existing conditions. (NOTE: A condition, recorded as pre-existing, that is intermittently symptomatic [e.g., headache] and which occurs during the study should be recorded as an adverse event);
- Drug interactions;
- Events occurring during diagnostic procedures or any washout phase of the study;
- laboratory or diagnostic test abnormalities occurring after the start of the study (i.e., after screening and once confirmed by repeat testing) that results in the withdrawal of the patient from the study, requires medical treatment or further diagnostic work-up, or is considered by the study investigator to be clinically significant. NOTE: Abnormal laboratory test results at the screening visit that preclude a patient from entering the study or receiving study treatment are not considered adverse events, but will be recorded to monitor data from patients who do not meet screening criteria.

The investigator must, for any common wart related AE, question the subject in detail to determine if there are any confounding factors (e.g., irritation by clothing or activity, sunburn) for any such AE.

The investigator should, when certain, report a diagnosis rather than the signs, symptoms or clinically relevant abnormal laboratory values associated with the AE. Otherwise, signs, symptoms or abnormal laboratory values may be used to describe the AE.

Any CS abnormality discovered prior to the first study medication treatment should be reported as medical history, not as an AE.

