13.1.3. Adverse Event Reporting Period

The investigator must start reporting non-serious AEs starting with the subject’s first study medication treatment continuing until the subject’s last study visit. Non-serious adverse events that occur between the time the subject was consented and the first application of study medication will be reported as medical history.

Reporting for SAEs begins after the subject signs the informed consent and continues until the subject’s last study visit (regardless of relationship to study medication). If a subject experiences a SAE after the subject’s last study visit, that is deemed by the investigator to be related to study medication, the investigator must report this to the Sponsor using the study specific SAE report form.

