13.2. Reporting Procedures

13.2.1. Procedures for Reporting Adverse Events

At each post enrollment visit, the investigator or designee will question the subject to elicit AEs using a non-directive question such as “Has there been any change in your health since the previous study visit?”

The Investigator/designee will monitor the subject for at least 20 minutes after the Treatment Completion Time at any visit during which a study medication treatment is performed to elicit AEs in a similar manner.

If appropriate, based on the subject's response to non-directed questioning regarding AEs, the investigator or designee will follow-up with directed questions and appropriate evaluations.

Any AE noted during the reporting period must be reported in the source documents and on the appropriate AE CRF.

AEs that are defined as “Not Related” to the study medications will be followed until they are resolved or until the subject's last study visit. AEs that are defined as “Related” to the study medications will be followed until they are resolved or, if not resolved after the subject's last study visit, until in the opinion of the investigator, the AE reaches a clinically stable outcome with or without sequelae.

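### Protocol 9.3 ties the adverse event question at the observation calls to the subject's own view of causality, contradicting the open question that 13.2.1 requires at the same visits

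*Protocol*

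**What the plan says.** Protocol 9.3 describes the three telephone visits for enrolled subjects who have no identified wart to treat. Staff are to "ask the subject if they have any adverse events that they feel are related to their previous treatment with A-101 Topical Solution", and also to ask about new and recurrent warts.

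Other parts of the protocol bear on the same calls:

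- Section 13.2.1: "At each post enrollment visit, the investigator or designee will question the subject to elicit AEs using a non-directive question such as" one about a change in the subject's health since the last visit. No exception is made for telephone visits or for untreated subjects.
- Section 13.1.1 defines an adverse event "whether or not considered related to the study drug".
- Section 13.1.3 requires serious events to be reported from consent to the last visit, "regardless of relationship to study medication".
- Section 13.1.5 gives the causality judgement to the investigator.
- Table 3, "Safety Observation Assessments for Subjects that are Clear at Visit 1 and Remain Clear", numbers the calls as Visits 2 to 4 and marks adverse events and concomitant therapies at each of them and at the in-office Day 182 visit.
- Table 3 footnote 2 words the content of the calls as "During the phone calls sites are to ask the subject if they have had any new warts develop" or have had a recurrence. It words no adverse event question.

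For subjects on the treatment schedule, Table 2 footnote 4 says the calls are "to assess for any safety issues and possible new concomitant medications the subject may have started taking".

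**The concern.** The study's primary objective is long-term safety. In 9.3, the section that describes these calls, the adverse event question is conditioned on what the subject attributes to a drug. A subject who was hospitalised, or fell ill, and does not connect this with earlier wart treatment can truthfully answer no. The investigator then never sees the event and cannot classify it.

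The wording for treated subjects' calls carries no such condition, so the two cohorts may be ascertained differently. Sites may also resolve the conflict with 13.2.1 in different ways. No later analysis can restore an event that was never elicited.

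**Working it through.** The plan states no figure for adverse event ascertainment, so the check is mainly a comparison of texts.

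| Contact | What the adverse event question covers | Source |
|---|---|---|
| Observation calls, Days 42, 84, 126 | Events the subject attributes to earlier A-101 | Protocol 9.3 |
| Same calls | Wart questions only | Table 3 footnote 2 |
| Same calls | Adverse event collection marked, no wording | Table 3 grid |
| Same calls, as Visits 2 to 4 | Open question | Protocol 13.2.1 |
| Treated subjects' calls, Days 15, 43, 102, 144 | Any safety issue | Table 2 footnote 4 |
| In-office visit, Day 182 | Open question | Protocol 13.2.1, Table 3 grid |

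**Which rule applies.** Both do. Section 9.3 does not exclude further questions, and 13.2.1 covers every visit after enrollment. A site that asks both questions complies with both sections. But 9.3 is the specific instruction for these calls and contains the only adverse event question worded for them. A site that works from 9.3, or from 9.3 with Table 3 footnote 2, would not be led to the open question.

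**Contacts and time covered.** After Day 1, the Table 3 grid has contacts on Days 42, 84, 126 and 182. Section 9.3 governs the first three, so 3 of 4. For a subject who stays untreated, these calls look back over 126 of 182 days: 126/182 = 0.69. A subject whose wart recurs moves to the Table 2 schedule and has a shorter span under 9.3.

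**Does Day 182 recover missed events?** Only in part. The example question in 13.2.1 looks back to the previous visit, which at Day 182 means Day 126, a span of 182 − 126 = 56 days. It is only an example, so a site could ask about a longer period.

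**Does the serious event rule recover them?** Under 13.2.2 the reporting duty starts when the investigator becomes aware of the event. It does not itself prompt the subject. The review of concomitant therapies at each call may reveal some events indirectly.

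**Number of subjects.** Protocol 14.1 expects 200 of 400 subjects to have had active treatment and 26% to be clear: 200 × 0.26 = 52, and 200 − 52 = 148, which reproduces the plan's 148. So about 52 former A-101 subjects would start in observation. The 26% is stated for warts, however, and a subject enters observation only if every wart is clear, so 52 is a rough guide. The number of former vehicle subjects who enter clear is not given.

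**Reach into the analysis.** Protocol 14.4 plans safety summaries for untreated subjects by parent-study arm. The SAP changes this. Safety summaries use subjects with at least one application (3.1, 3.11), show only the two treated groups (3.2), and leave never-treated subjects to listings (3.14). For subjects treated later, events with onset before the first application are classed as prior and stay out of the treatment-emergent tables (3.11.2).

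**The case against.** The strongest reply is that the protocol already requires what is asked for. Section 13.2.1 applies to these calls, Table 3 schedules adverse event collection at each, serious events are reportable whatever their cause, and the SAP tabulates no adverse event rate for untreated subjects. All of this stands, and it limits the point to a contradiction that creates a risk. It does not remove the contradiction, because the specific instruction and the general one differ and neither is said to prevail.

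A second reply is that 13.1.3 starts non-serious reporting at the first study medication treatment. Read literally, an observation subject's non-serious events are not reportable adverse events, however the question is put. That is a separate ambiguity, and it narrows the immediate effect to serious events and to whatever is recorded as medical history.

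A reader might infer more than the documents support:

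- That observation subjects are asked only about events they think related. Section 9.3 does not say so, and 13.2.1 requires more.
- That causality is handed to the subject. Under 13.1.5 the investigator still classifies every event that is reported; the risk lies in events that never reach the investigator.
- That a stated percentage of events is lost. This needs the rate at which subjects attribute events to the drug, which the documents do not give, and it would assume that 13.2.1 is ignored.
- That an untreated vehicle reference group is distorted. The SAP no longer tabulates that group, and the documents give neither its size nor whether its members knew their parent-study assignment when called.

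**Conclusion.** The point holds as an internal contradiction. Section 9.3 conflicts with the open questioning of 13.2.1 and sits badly with 13.1.1, 13.1.3 and the wording for treated subjects' calls; Table 3 footnote 2 does not settle it. The loss arises if sites follow 9.3 literally, and can then affect three of the four contacts after Day 1. Ascertainment may differ between cohorts and across the roughly 50 sites.

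The effect on the SAP's treatment-emergent tables should be small. One indirect route remains: a condition missed in observation could later be recorded as new after treatment starts. The main exposure is in serious event capture, in the listings that hold the untreated subjects' safety data, and in any summaries still produced under Protocol 14.4. The number of events lost cannot be estimated from the documents. The conclusion rests on the wording and does not depend on the approximate 52 subjects.

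**What to change.** In Protocol 9.3, replace the attribution clause with the non-directive question of 13.2.1 and remove the reference to previous A-101 treatment. Add the same question to Table 3 footnote 2. Keep the questions on new and recurrent warts, and leave relatedness to the investigator under 13.1.5. It would help to state in 13.1.3, at the same time, when non-serious reporting starts for subjects who are not treated in this study.

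The core change is one sentence in 9.3, one addition to a footnote, and matching wording in the sites' call instructions. It needs no extra visits or staff. The downside is that a few more unrelated events will be recorded and followed.
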